#### **9.2.2.4. Allergic/Hypersensitivity Reactions**

All allergic or hypersensitivity reactions will be reported by the investigator as either AEs or, if any serious criterion is met, as SAEs. Additional data, such as type of reaction and treatment received, will be collected on any AEs or SAEs that the investigator deems related to study drug via an eCRF created for this purpose. At the time of AE occurrence, a sample will be collected for measurement of dulaglutide anti-drug antibodies (ADA). Study drug should be temporarily interrupted in any individual suspected of having a severe or serious allergic reaction to study drug (Section 8.1.2). Study drug may be restarted when/if it is safe to do so, in the opinion of the investigator. If study drug is permanently discontinued, see Section 8.1.1 for procedures required in this situation.

#### **9.2.2.5. Supraventricular Arrhythmias and Cardiac Conduction Disorders**

All events of treatment-emergent supraventricular arrhythmias and cardiac conduction disorders will be fully evaluated. Patients who develop any event from these groups of disorders should undergo an ECG which should be submitted to the central reading center. Additional diagnostic tests to determine exact diagnosis should be performed, as needed. The specific diagnosis will

be recorded as an AE. Events that meet criteria for serious conditions as described in Section 9.2.1 must be reported as SAEs. Study drug should be temporarily discontinued in any patient with signs and symptoms of serious cardiac arrhythmias or conduction disorders. Study drug may be restarted when/if it is safe to do so, in the opinion of the investigator.

### **9.2.3. Complaint Handling**

Lilly collects product complaints on investigational products and drug delivery systems used in clinical studies in order to ensure the safety of study participants, monitor quality, and to facilitate process and product improvements.

Patients will be instructed to contact the investigator as soon as possible if he or she has a complaint or problem with the investigational product so that the situation can be assessed.

## **9.3. Treatment of Overdose**

Study drug overdose (more than the specified number of injections, whether for placebo or dulaglutide treatment) will be reported as an AE. In the event of overdose, refer to the IB and or Product Label.

## **9.4. Safety**

### **9.4.1. CV Safety**

#### **9.4.1.1. Cardiovascular Events**

Deaths and nonfatal CV AEs will be adjudicated by a committee of physicians external to Lilly with cardiology expertise. The nonfatal CV AEs to be adjudicated include: MI; hospitalization for unstable angina; hospitalization for heart failure; coronary interventions (such as coronary artery bypass graft or percutaneous coronary intervention); and cerebrovascular events, including cerebrovascular accident (stroke) and transient ischemic attack.

#### **9.4.1.2. Electrocardiograms**

To assess the effect of higher doses on cardiac electrophysiology, ECGs will be collected according to the Schedule of Activities (Section 2) and centrally overread. Electrocardiograms should be recorded in triplicate according to study-specific recommendations included in the Manual of Operations for the study, using standardized equipment provided by the sponsor.

Each ECG tracing will be assessed by the investigator immediately upon recording for clinical management purposes. Any clinically significant findings from ECGs that result in a diagnosis and that occur after the patient receives the first dose of the investigational treatment should be reported to Lilly or its designee as an AE via eCRF. Results of the central overread will be entered into the clinical trial database and will be used for the statistical analysis of the effects of the randomized treatments. In addition, once the overread ECG is returned from the centralized ECG vendor, the investigator, or qualified designee, is responsible for determining if any change to the patient management is needed. The investigator, or qualified designee, must document his/her review of the ECG printed at the time of evaluation, the final overread ECG report issued by the central ECG laboratory, and any alert reports.

#### **9.4.1.3. Vital Signs**

Sitting BP and pulse rate (PR) will be measured using standardized equipment provided by the sponsor according to the Schedule of Activities (Section 2). Vital sign measurements should be taken before obtaining an ECG tracing and before collection of blood samples for laboratory testing, at visits where required (see Schedule of Activities, Section 2). The participant should be required to sit quietly for 5 minutes before vital sign measurements are taken. An appropriately sized cuff (cuff bladder encircling at least 80% of the arm) should be used to ensure the accuracy of BP measurements. The arm used for the BP measurement should be supported at heart level. At Visit 1 (screening), to determine which arm should be used to collect BP and PR throughout the study, BP and PR will be measured once in each arm, and the arm that had the higher systolic BP should be used to collect all 3 measurements of both BP and PR at all study visits. For each parameter (PR, systolic blood pressure [SBP], and DBP), 3 measurements will be taken using the same arm; the recordings should be taken at least 1 minute apart, and each measurement of sitting PR and BP will be recorded in the eCRF. Any AE related to changes in BP and PR should be reported.

#### **9.4.2. Laboratory Tests**

For each patient, laboratory tests detailed in [Appendix 2](#) should be conducted according to the Schedule of Activities (Section 2).

Any clinically significant findings from laboratory tests that result in a diagnosis and that occur after the patient receives the first dose of investigational product should be reported to Lilly or its designee as an AE via eCRF.

#### **9.4.3. Safety Monitoring**

Lilly will periodically review evolving aggregate safety data within the study by appropriate methods, including trends in safety variables, laboratory analytes, and AEs. An AC will review prespecified safety reports in an unblinded fashion. In addition, the study team will review safety reports in a blinded fashion according to the schedule provided in the Trial-Level Safety Review plan. Lilly will also review SAEs within time frames mandated by company procedures. The Lilly CRP will, as appropriate, consult with the functionally independent Global Patient Safety therapeutic area physician or clinical scientist.

In addition, specific safety measures are included in the protocol to ensure appropriate monitoring of pancreatic, thyroid, and liver safety. Laboratory findings that trigger pancreatic and thyroid safety monitoring per Lilly standards are provided in Sections [9.2.2.2](#) and [9.2.2.3](#), respectively. Details of liver safety monitoring are provided in [Appendix 4](#). If a study patient experiences elevated ALT  $\geq 3 \times$  ULN, alkaline phosphatase  $\geq 2 \times$  ULN, or elevated total bilirubin  $\geq 2 \times$  ULN, clinical and laboratory monitoring should be initiated by the investigator per Lilly Hepatic Safety Monitoring Algorithm. Details for hepatic monitoring depend upon the severity and persistence of observed laboratory test abnormalities. To ensure patient safety and comply with regulatory guidance, the investigator is to consult with the Lilly CRP regarding collection of specific recommended clinical information and follow-up laboratory tests. See [Appendix 4](#).

## 9.5. Pharmacokinetics

Blood samples for determining plasma concentrations of dulaglutide, associated with time from dose, will be obtained at selected visits from all patients in accordance with the Study Schedule and at ET (see Schedule of Activities [Section 2]). However, only samples from patients assigned to treatment with dulaglutide will be analyzed for drug concentrations.

Timing of PK blood draws have been optimized for sparse sampling using a standard PK optimal sampling approach. Pharmacokinetic samples will be drawn to include a range of sampling time windows (predose, and 1-24 hours, 24-96 hours, and 120-168 hours postdose) spread over several clinic visits. For the ET visit, a sample may be drawn at any time during the visit. The study has been designed so that, where possible, each immunogenicity sample will be accompanied by a PK sample in the same visit. At visits where ECG measurements are taken, these should be accompanied by a time-matched PK sample within 30 minutes (before or after), during the same visit.

At the visits and times specified in the Schedule of Activities (Section 2), venous blood samples of approximately 4 mL each will be collected to determine the plasma concentrations of dulaglutide.

Instructions for the collection and handling of blood samples will be provided by the sponsor. The actual date and time (24-hour clock time) of each sampling and all study drug doses must be clearly recorded.

Drug concentration information that would unblind the study will not be reported to investigative sites or blinded personnel until the study has been unblinded.

Bioanalytical samples collected to measure investigational product concentration will be retained for a maximum of 1 year following last patient visit for the study.

## 9.6. Pharmacodynamics

Pharmacodynamic parameters will include safety and efficacy endpoints as described in Section 4. Analysis methods are described in Section 10.3.5.

## 9.7. Pharmacogenomics

### 9.7.1. Whole Blood Samples for Pharmacogenetic Research

A whole blood sample will be collected for pharmacogenetic analysis as specified in the Schedule of Activities (Section 2) where local regulations allow.

Samples will not be used to conduct unspecified disease or population genetic research either now or in the future. Samples will be used to investigate variable response to dulaglutide and to investigate genetic variants thought to play a role in T2D and related complications. Assessment of variable response may include evaluation of AEs or differences in efficacy.

All samples will be coded with the patient number. These samples and any data generated can be linked back to the patient only by the investigator site personnel.

Samples will be retained for a maximum of 15 years after the last patient visit for the study, or for a shorter period if local regulations and/or ERBs/investigational review boards impose shorter time limits, at a facility selected by Lilly or its designee. This retention period enables use of new technologies, response to regulatory questions, and investigation of variable response that may not be observed until later in the development of dulaglutide or when dulaglutide is widely commercially available.

Molecular technologies are expected to improve during the 15-year storage period and therefore cannot be specifically named. However, existing approaches include whole genome or exome sequencing, genome-wide association studies, and candidate gene studies, and epigenetic analyses. Regardless of technology utilized, genotyping data generated will be used only for the specific research scope described in this section.

## **9.8. Biomarkers and Antibodies**

### **9.8.1. Samples for Immunogenicity Research**

Samples from patients in each treatment arm will be tested for the development of treatment-emergent dulaglutide ADA, defined as 4-fold increase in titer from baseline. A blood sample will be collected at specific study visits according to the Schedule of Activities (Section 2).

Treatment-emergent positive dulaglutide ADA samples will be evaluated for their ability to neutralize the activity of assigned treatment (dulaglutide-neutralizing antibodies). Positive dulaglutide ADA samples may also be tested for cross-reactivity with native GLP-1, and if positive, then for neutralizing antibodies against native GLP-1.

Samples will be retained for a maximum of 15 years after the last patient visit for the study, or for a shorter period if regulations and ERBs impose shorter time limits, at a facility selected by Lilly or its designee. The duration allows the sponsor to respond to future regulatory requests related to dulaglutide.

### **9.8.2. Biomarkers**

Biomarker research is performed to address questions of relevance to drug disposition, target engagement, PD, mechanism of action, variability of subject response (including safety), and clinical outcome. Sample collection is incorporated into clinical studies to enable examination of these questions through measurement of biomolecules including DNA, RNA, proteins, lipids, and other cellular elements.

Serum and plasma samples (ethylenediaminetetraacetic acid [EDTA] and remaining P800 plasma from glucagon collection) for nonpharmacogenetic biomarker research will be collected at the times specified in the Schedule of Activities (Section 2) where local regulations allow.

Samples will be used for research on the drug target, disease process, variable response to dulaglutide, pathways associated with diabetes mellitus, mechanism of action of dulaglutide, and/or research method, or for validating diagnostic tools or assay(s) related to diabetes mellitus.

All samples will be coded with the subject number. These samples and any data generated can be linked back to the subject only by the investigative site personnel.

Samples will be retained for a maximum of 15 years after the last subject visit, or for a shorter period if local regulations and/or ERBs impose shorter time limits, at a facility selected by Lilly. This retention period enables use of new technologies, response to regulatory questions, and investigation of variable response that may be not observed until later in the development of dulaglutide or after dulaglutide is commercially available.

### **9.9. Health Economics**

Not applicable.

## 10. Statistical Considerations

### 10.1. Sample Size Determination

Assuming a screen failure rate of 30%, approximately 429 patients will need to be screened to attain approximately 300 patients randomized to the 4 treatment arms in a 1:1:1:1 ratio for 4.5 mg, 3.0 mg, 1.5 mg dulaglutide, or placebo weekly (~75 patients per arm). For the investigational dulaglutide dose arms (4.5 mg and 3.0 mg), approximately 38 patients will be assigned to each titration algorithm (Algorithms 1 and 2). Assuming a 20% dropout, this will result in approximately 60 patients per arm and 30 patients per algorithm (in each of the investigational-dose dulaglutide arms) completing the study.

The aforementioned sample size provides  $\geq 90\%$  power to demonstrate superiority for the dulaglutide doses (4.5 mg, 3.0 mg, and 1.5 mg) to placebo with respect to HbA1c change from baseline to 18 weeks. This assumes a true glycemic effect difference of -1% HbA1c for each dulaglutide dose versus placebo, and a standard deviation (SD) of 1.2% with a 2-sided alpha of 0.05.

### 10.2. Populations for Analyses

Table GBGJ.4 defines the populations to be used for analyses.

**Table GBGJ.4. Populations for Analyses**

Population	Description
Entered	All participants who sign informed consent
Intent-to-treat (ITT)	All participants who are randomized and take at least 1 dose of study medication for an assigned treatment arm
All randomized population	All patients who are randomized
Per protocol	All ITT patients who meet all of the following criteria: 
 
• Have no important protocol deviation that could impact the assessment of the primary endpoint*
 
• At least 75% compliant with study drug administration
 
• Complete the treatment period (18 weeks)
 
• Have a value of the primary efficacy measure (HbA1c) at 18 weeks
 

Completer set	All ITT patients who complete 18 weeks of study drug treatment without rescue therapy

Abbreviation: HbA1c = hemoglobin A1c.

\*Full list will defined in the Statistical Analysis Plan.

### 10.3. Statistical Analyses

#### 10.3.1. General Statistical Considerations

Statistical analysis of this study will be the responsibility of Lilly or its designee. Any change to the data analysis methods described in the protocol will require an amendment ONLY if it changes a principal feature of the protocol. Any other change to the data analysis methods described in the protocol, and the justification for making the change, will be described in the

clinical study report (CSR). Additional exploratory analyses of the data will be conducted as deemed appropriate.

Unless otherwise specified, listings will include all randomized patients. Efficacy and safety analyses will be conducted in the intent-to-treat (ITT) population. The primary efficacy measure (change from baseline in HbA1c) will also be evaluated in the PP population and Completer sets. In all efficacy and hypoglycemia analyses, all data after rescue therapy will be censored. Analyses of safety parameters, except for hypoglycemia events, will be conducted in the ITT population including the post-rescue therapy data.

Countries with fewer than 10 randomized patients will be pooled for statistical analyses. Pooled country will be employed for all formal statistical model-based analyses.

Unless otherwise specified, all tests of treatment effects will be conducted at a 2-sided alpha level of 0.05, and confidence intervals (CIs) will be calculated at 95%, 2-sided. All tests of interactions between treatments and factors of interest will be conducted at a 2-sided alpha level of 0.10.

The baseline visit will be Visit 3. For all variables, including HbA1c, if baseline data are not available or are missing, the last nonmissing measurement taken prior to this visit will be used for the baseline measurement. The measurement for the primary analysis is defined as the change from baseline in HbA1c to Week 18 (Visit 12).

For all statistical analyses, missing data will be treated as missing at random; therefore, no imputation is needed unless otherwise stated.

A mixed-model repeated measures (MMRM) analysis will be used to analyze continuous longitudinal variables. In this model, restricted maximum likelihood will be used to obtain model estimates with Kenward-Roger option to estimate denominator degrees of freedom. The corresponding baseline value will be used as a covariate, and the stratification factor (HbA1c <8% or ≥8%), pooled country, treatment, visit, and treatment-by-visit interaction will be fixed effects. For HbA1c change from baseline analysis, stratification factor will be removed from the aforementioned model. An unstructured covariance structure will be used to model the within-patient errors. If this model fails to converge, the following covariance structures will be tested in order:

- Toeplitz with heterogeneity
- autoregressive with heterogeneity, by visit
- compound symmetry with heterogeneous variances by visit
- Toeplitz
- autoregressive
- compound symmetry without heterogeneous variances, by visit.

The first covariance structure that converges will be used.

For continuous laboratory measurements for safety, an analysis of variance (ANOVA) on ranks will be used with treatment as a fixed effect.

For all continuous measures, summary statistics will include number of patients, mean, SD, median, minimum, and maximum for both the actual and change from baseline measurements at each scheduled visit for each treatment. Least-squares mean (LS mean) and standard errors (SEs) derived from the model will also be displayed for the change from baseline measurements at each scheduled visit for each treatment. Treatment comparisons will be displayed showing the treatment difference LS mean and the 95% CIs between each dose and placebo, and between each investigational dose and 1.5 mg at the same visit, along with the corresponding p-values.

Summary statistics for categorical measures will include number of subjects and percentages. The percentage of patients achieving target HbA1c <7.0% at Week 18 will be analyzed using a longitudinal logistic regression with repeated measurements with treatment, visit, treatment-by-visit interaction, and baseline HbA1c-by-visit interaction as fixed effects and baseline HbA1c as a covariate. For the analysis of other categorical measures, Fisher's exact test will be used for treatment comparisons, unless 80% of cells have an expected value of at least 5, in which case the Chi-square test will be used unless otherwise stated.

No adjustments for multiplicity will be performed.

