## **7.2. Method of Treatment Assignment**

Patients who meet all criteria for enrollment will be randomized to 1 of the study treatment arms at Visit 3. Assignment to treatment arms will be determined by a computer-generated random sequence using an IWRS. The IWRS will be used to assign cartons containing double-blind study drug to each patient. Site personnel will confirm that they have located the correct cartons by entering a confirmation number found on the label into the IWRS.

Block randomization will be used at the country level. Patients will be randomized in a 1:1:1:1 ratio (dulaglutide 4.5 mg, dulaglutide 3.0 mg, dulaglutide 1.5 mg, placebo). Within the dulaglutide 4.5 mg and 3.0 mg arms, patients will be randomly assigned (1:1) to Algorithm 1 or Algorithm 2. Randomization will be stratified by HbA1c (<8%, ≥8%).

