6.1. General Considerations

Statistical analysis of this study will be the responsibility of Eli Lilly and Company or its designee. Any change to the data analysis methods described in the protocol will require an amendment ONLY if it changes a principal feature of the protocol. Any other change to the data analysis methods described in the protocol, and the justification for making the change, will be described in the statistical analysis plan (SAP) or the clinical study report (CSR). Additional exploratory analyses of the data may be conducted as deemed appropriate without further changes made to the protocol or SAP even after the datalock.

Countries with fewer than 10 randomized patients will be pooled for statistical analyses. Pooled country will be employed for all formal statistical model-based analyses as a block factor unless otherwise denoted.

Unless otherwise specified, all tests of treatment effects will be conducted at a 2-sided alpha level of 0.05, and confidence intervals (CIs) will be calculated at 95%, 2-sided. All tests of interactions between treatments and factors of interest will be conducted at a 2-sided alpha level of 0.10. No adjustments for multiplicity will be performed.

The baseline visit will be Visit 3. For all variables, including HbA1c, if baseline data are not available or are missing, the last nonmissing measurement taken prior to this visit will be used for the baseline measurement. The efficacy measure for the primary analysis is defined as the change from baseline in HbA1c to Week 18 (Visit 12).

For all statistical analyses, missing data will be treated as missing at random unless otherwise specified; therefore, no imputation is needed unless otherwise stated.

The treatment groups mentioned in this document are based on the randomized treatment groups: dulaglutide 4.5 mg, dulaglutide 3.0 mg, dulaglutide 1.5 mg, placebo. For the purposes of tables, figures, the treatment groups will be: Dula 4.5, Dula 3.0, Dula 1.5, and Placebo. For data listings, the treatment groups will be presented as Placebo, Dula 1.5, Dula 3.0/A1 representing dulaglutide 3.0 mg/algorithm 1, Dula 3.0/A2 representing dulaglutide 3.0 mg/algorithm 2, Dula 4.5/A1 representing dulaglutide 4.5 mg/algorithm 1, Dula 4.5/A2 representing dulaglutide 4.5 mg/algorithm 2.

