6.2. Adjustments for Covariates

The study is stratified by baseline HbA1c with country as a block factor; therefore, both stratification factors will be fitted in the corresponding statistical model as fixed effects for the non-HbA1c measurements unless otherwise stated. For HbA1c analysis, the strata of baseline HbA1c will be replaced with the covariate of baseline HbA1c. For other continuous variables other than some safety laboratory measures, a corresponding baseline measure will be added as a covariate.

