6.11.2.3. Bayesian Analyses For Exploratory Objectives

A Bayesian integrated 2-component prediction (ITP) model (Fu and Manner 2010) will be fitted for the primary endpoint separately in ITT population by censoring all post rescue therapy data,

and in ITT population including all available data regardless of rescue medication or adherence to the study drug. Non-informative priors will be used in this model. In addition, the informative priors from the posterior for placebo and posterior for dulaglutide 1.5 mg obtained from Study H9X-MC-GBCF (GBCF) and Study H9X-MC-GBDE (GBDE) will be evaluated in this model to check the robustness of the analysis.

$$Y_{ijt} = (\theta_i + S_{ij} + \alpha \times (B_{ij} - \bar{B}) + \varepsilon_{ijt}) \times \left(\frac{1 - e^{k_i \times t}}{1 - e^{k_i \times 18}} \right)$$

Prior information: $\theta_i, \alpha \sim N(0, 3)$; $S_{ij}, \varepsilon_{ijt} \sim \text{uniform}(0.01, 3)$; $k_i \sim \text{uniform}(-1, 1)$ where Y_{ijt} represents HbA1c change from baseline from dose i , subject j at time t . Parameter θ_i is the predicted drug effect of dose i at 18-week therapy. The parameter S_{ij} is a random between-subject SD, and ε_{ijt} is the within subject SD. The B_{ij} is baseline HbA1c for subject j at dose i and \bar{B} is the overall arithmetic mean baseline HbA1c from all subjects. k_i is the parameter to represent how fast to reach the effect for dose i at Week 18.

Probabilities based on posterior distributions of the parameter of interest: change from baseline to Week 18, and Week 26 will be generated from this model using 10000 MCMC samples with thin=10 and burn-in=10000:

$$\text{pr}(\Delta_i - \Delta_{\text{dula1.5mg}} < \text{threshold})$$

i stands for dulaglutide 3.0 mg or 4.5 mg.

The threshold of -.15, -.2, and -.3% will be used, separately.

If this model fails to converge, an alternative Bayesian model will be fitted:

$$y_{ijt} \sim MVN(\mu[i, t], \Omega)$$

$$u[i, t] = \alpha \times (B[i, t] - \bar{B}_0) + \beta[i, t] \times T[i, t]$$

Where $\beta[i, t]$ is the effect for dose i at time t . Ω is the variance-covariance matrix.

The priors for each parameters are: $\alpha \sim N(0, 3)$, $\beta[i, t] \sim N(0, 3)$, $\Omega \sim \text{wishart}(t, t\text{-demension Identity matrix})$.

The probability for Week 26 will be assumed to be the same as Week 18 from this model.

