6.14. Subgroup Analyses

Subgroup analyses of the treatment interaction for important factors, including age group, race, gender, country, duration of diabetes ($<$ median, \geq median), baseline HbA1c ($< 8\%$, $\geq 8\%$), and BMI ($<$ median, \geq median), may be conducted for the primary endpoint of HbA1c. Country will use the pooled country.

These will be conducted using the MMRM with treatment, visit, subgroup, treatment-by-visit, treatment-by-subgroup, visit-by-subgroup, and treatment-by-visit-by-subgroup as fixed effects, and baseline as a covariate. If the MMRM fails to converge, the corresponding analysis of covariance (ANCOVA) or ANOVA model (LOCF) will be used.

When analyzing baseline HbA1c as a subgroup, the baseline HbA1c will not be included as a covariate to avoid colinearity.

TEAE exceeding 5% will be summarized descriptively for the patients with the top quartile of the body weight reduction from baseline by treatment group.

Other exploratory subgroup analyses may be performed as deemed appropriate.

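### Randomisation is blocked by country, but the Bayesian dose-comparison models and the subgroup MMRM leave pooled country out without a stated reason; the likely loss of precision is small

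*Protocol*

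**What the plan says.** Protocol 7.2 states "Block randomization will be used at the country level" and adds stratification by HbA1c below or at least 8%. SAP 6.2 describes the design in the same way: "The study is stratified by baseline HbA1c with country as a block factor".

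Protocol 10.3.1 gives the analysis rule with no exception: "Pooled country will be employed for all formal statistical model-based analyses". SAP 6.1 repeats it with one: "Pooled country will be employed for all formal statistical model-based analyses as a block factor unless otherwise denoted". SAP 6.2 has a similar proviso.

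The specified models follow the rule unevenly:

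- **Country included:** the general MMRM, which serves the primary analysis (protocol 10.3.1, SAP 6.1); the HbA1c-target model (SAP 6.11.3.1); the hypoglycaemia-rate model (SAP 6.13.4.1); and the pancreatic-enzyme MMRM (SAP 6.13.4.3).
- **Country absent, Bayesian:** in SAP 6.11.2.3 the ITP response "represents HbA1c change from baseline from dose" is built from a dose effect, a subject term, centred baseline, a residual and a time-course factor. The multivariate-normal fallback has baseline, dose-by-time effects and a covariance matrix. SAP 6.11.3.3 reuses both for body weight, and 6.13.7.2 and 6.13.7.3 reuse the fallback for heart rate and pulse rate.
- **Country absent, subgroups:** SAP 6.14 says "These will be conducted using the MMRM with treatment, visit, subgroup, treatment-by-visit, treatment-by-subgroup, visit-by-subgroup, and treatment-by-visit-by-subgroup as fixed effects", with baseline as covariate. Protocol 10.3.6 lists the same terms. Pooled country enters only when it is the subgroup.

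**The concern.** When arms are balanced within country by design, a model without country leaves the treatment contrast essentially unchanged but counts between-country variation as residual error. The stated uncertainty is then somewhat larger than the design delivers.

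The Bayesian models are where this matters most. They produce the probabilities against 1.5 mg that guide Phase 3 dose selection, and protocol 5.4 turns to Bayesian methods because the sample is too small for frequentist ones. SAP 6.16.2.2 sets a numeric interim criterion of the same form: at least 80% probability that a higher dose beats 1.5 mg by at least 0.2% HbA1c. MMRM results are reported alongside, so the two HbA1c analyses would differ in adjustment as well as in method.

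**Working it through.** **Plan's own figures.** Protocol 10.1 gives a difference of 1.0%, SD 1.2%, two-sided alpha 0.05, 75 randomised per arm and 20% dropout. Completers are 75 × 0.8 = 60 per arm, and 300/0.7 ≈ 429 screened. Power at 60 per arm is 99.5%, and 31 per arm would give 90%, so the claim of at least 90% is correct. The plan states no interval width or posterior SD for the models at issue.

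**Assumptions.** The documents do not give r, the share of outcome variance that country explains beyond baseline, or the number of countries. I take r = 0 to 10% and 3, 6 or 12 countries. The SD of 1.2% was planned for comparisons with placebo; using it against 1.5 mg is a further assumption.

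**Width.** With balance within country:

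- SE without country = SD × √(2/n) = 1.2 × √(2/60) = 0.2191, so the 95% half-width is 1.96 × 0.2191 = 0.429.
- SE with country = SD × √(1 − r) × √(2/n), so omission widens the interval by the factor 1/√(1 − r).

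| r (assumed) | Half-width with country | Widening from omission |
|---|---|---|
| 0% | 0.429 | 0% |
| 2% | 0.425 | 1.0% |
| 5% | 0.419 | 2.6% |
| 10% | 0.407 | 5.4% |

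**Simulation.** A linear model with 240 patients in four country-blocked arms (1,500 runs per setting) gave mean width ratios, omitted to included, of:

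- 1.00 at r = 0
- about 1.01 at 2%
- about 1.02 at 5%
- 1.04 to 1.05 at 10%

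At r = 0 the model without country gave the narrower interval in 57% to 64% of runs. The subgroup MMRM and the ITP model were not simulated; the same variance argument is applied to them.

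**Posterior probability.** Under a flat prior and normal approximation for one dose, Pr(difference < −0.2) = Φ((−0.2 − d)/SE), where d is the observed difference. At r = 10% the SE at 60 per arm falls from 0.2191 to 0.2078. At the interim (120 completers, 30 per arm) it falls from 0.3098 to 0.2939.

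| Case | Without country | With country |
|---|---|---|
| Final, d = −0.4 | 0.819 | 0.832 |
| Final, d = −0.1 | 0.324 | 0.315 |
| Interim, d = −0.4 | 0.741 | 0.752 |

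Omission pulls the probability towards 50% from either side.

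**Interim threshold.** The d needed for 80% is −0.2 − 0.842 × SE. This is −0.461 without country and −0.447 with it.

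**The case against.** The strongest reply is that specific text overrides general text. A written equation and an explicit term list can be read as the exceptions that SAP 6.1 and 6.2 allow. Protocol 10.3.1 itself specifies treatment-only rank analyses and an HbA1c-target model without country, so its rule reads as a default. Whether the rule's wording on formal analyses reaches these models is also open: the ITP model is called supportive, its SAP sections are labelled exploratory, and the subgroup analyses are optional. This stands to the extent that the omission is permitted. A reader might infer that the SAP breaches the protocol, but the documents do not establish that. They show a mismatch with no reason given, although SAP 6.11.3.1 restores country to the HbA1c-target model where the protocol's list lacked it.

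A reader might also infer that the intervals are certainly too wide. That depends on a variance share the documents do not give, and at 0% there is nothing to gain. Nor would a 10% share amount to discarding 30 of 300 patients: a contrast with 1.5 mg uses two arms, about 120 completers, so 10% is about 12.

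The width formula is an upper simplification. HbA1c strata, algorithm sub-assignment, pooling of small countries and dropout make the balance only approximate, and the informative-prior runs have a posterior SD that also depends on the prior.

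**Conclusion.** The mismatch is real and can be read directly from the texts. Its consequence is conditional and small: widening of about 0% to 5% for country shares of 0% to 10%, and shifts of about 0.01 in posterior probability at 10% in the cases computed. The interim threshold moves by 0.014 percentage points of HbA1c (0.461 − 0.447). These figures rest on the assumed share, the planned SD, near-balance within country and a single-dose flat-prior approximation.

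A reader might infer that the dose-selection decision or the primary result is compromised. Neither follows. The primary MMRM contains pooled country and its power is untouched, and the assessment committee also weighs the safety data. This is a worthwhile refinement of low severity: the trial already blocks on country and records it, and the plan adjusts for it elsewhere.

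**What to change.** - **SAP 6.11.2.3, both models:** add a pooled-country effect beside the baseline term, with a vague prior. Centre it so that theta, which "is the predicted drug effect of dose i at 18-week therapy", remains the average dose effect and stays comparable with the GBCF and GBDE priors. Carry the change into 6.11.3.3, 6.13.7.2 and 6.13.7.3.
- **Protocol 10.3.6 and SAP 6.14:** add pooled country as a fixed effect, except where country is the subgroup.
- **If the sponsor prefers not to adjust:** name these models as exceptions in SAP 6.1 and give the reason.

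The wording should be settled before the efficacy interim, so that adjustment is not chosen after seeing results.

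Costs: a few degrees of freedom, with marginally wider intervals if country has no effect; a check that the informative priors still match theta; slightly more convergence risk in a subgroup MMRM that already has a three-way interaction and falls back to LOCF models; and a wording change in the protocol as well as the SAP.
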